### 6.2.2 Exclusion Criteria

The presence of any of the following will preclude patient inclusion:

1. Age < 15 years (age < 18 years at centres that do not treat paediatric patients).
2. Exclusions related to medication:  
Previous therapy with:
  - a. Any biological B cell depleting agent (such as rituximab or belimumab) within the past 6 months.
  - b. Alemtuzumab or anti-thymocyte globulin (ATG) within the last 12 months.
  - c. IVIg, infliximab, etanercept, adalimumab, abatacept or plasma exchange in past 3 months.
  - d. Any investigational agent within 28 days of screening, or 5 half-lives of the investigational drug (whichever is longer).
3. Exclusions related to general health:
  - a. Significant or uncontrolled medical disease not related to AAV, which in the investigators opinion would preclude patient participation.
  - b. Presence of another multisystem autoimmune disease, including Churg Strauss syndrome, systemic lupus erythematosus, anti-GBM disease, or cryoglobulinaemic vasculitis.
  - c. Any concomitant condition anticipated to likely require greater than 4 weeks per year of oral or systemic glucocorticoid use and which would preclude compliance with the glucocorticoid protocol (e.g. poorly-controlled asthma, COPD, psoriasis, or inflammatory bowel disease).
  - d. History of severe allergic or anaphylactic reactions to humanised or murine chimeric monoclonal antibodies.
  - e. Known infection with HIV (HIV testing will not be a requirement for trial entry); a past or current history of hepatitis B virus or hepatitis C virus infection.
  - f. Ongoing or recent (last 12 months) evidence of active tuberculosis or known active infection (screening for tuberculosis is part of 'standard of care' in patients with established AAV) or evidence of untreated latent tuberculosis. Screening for tuberculosis is as per local practice.
  - g. History of malignancy within the past five years or any evidence of persistent malignancy, except fully excised basal cell or squamous cell

carcinomas of the skin, or cervical carcinoma in situ which has been treated or excised in a curative procedure.

- h. Pregnancy or inadequate contraception in women of childbearing potential.
  - i. Breast feeding or lactating.
  - j. Medical, psychiatric, cognitive or other conditions that, in the investigator's opinion, compromise the patient's ability to understand the patient information, to give informed consent, to comply with the trial protocol, or to complete the study.
4. Exclusion criteria related to laboratory parameters:
- a. Bone marrow suppression as evidenced by a total white count  $< 4 \times 10^9/l$ , haemoglobin  $< 7 \text{ gm/dl}$  or platelet count  $< 100,000/\mu l$ .
  - b. Aspartate aminotransferase or alanine aminotransferase or amylase  $> 2.5$  times the upper limit of normal, unless attributed to vasculitis.

### 6.3 Randomisation and Blinding

(ICH E3; 9.4.3, 9.4.6. ICH E9; 2.3.1, 2.3.2)

This is an open-label (unblinded) study. Patients who achieved disease control by month 4 ( $BVAS/WG \leq 1$  and daily prednisone dose  $\leq 10\text{mg}$ ) will be randomised 1:1 to receive either rituximab or azathioprine. A blocked randomisation will be performed, using a block size of 6. Patients will be stratified at the time of randomisation according to:

1. ANCA type (anti-PR3 or anti-MPO).
2. Relapse severity (severe or non-severe).
3. Selected prednisone induction regimen (1A or 1B).

Randomisation will be performed using a web-based system (TENALEA). This will be accessed by the principal investigator (PI) and suitably trained site staff through a secure, person specific log-in.

### 6.4 Study Schedule

(ICH E3; 9.5.1. ICH E9; 2.2.2)

Table 2 illustrate the schedule of events for the entire trial. The induction phase of the trial comprises the first 4 months from enrolment. At month 4 patients who have achieved remission are randomised to either maintenance therapy with rituximab or azathioprine. The maintenance phase of the trial, comprising 20

months of treatment and a 12–24 months follow up phase, commences at month 4 from enrolment.

Completed Case Report Forms (CRFs) are expected to be returned to the trial coordinating centre within 2 weeks of evaluation and the Data Manager routinely queries sites for missing/delayed forms.

Important notes regarding the schedule of events:

- The Screening and Month 0 visits must take place within 2 weeks of each other.
- The Treatment Form at Month 0 visit is completed by the PI at weeks 1, 2, 3 and 4 for rituximab infusion.
- Laboratory tests results are permitted to be within  $\pm 2$  weeks of the date of the study evaluation.
- Unscheduled assessments are performed at the time of relapse or study termination/withdrawal. Unscheduled assessment are retained for safety reviewing and not incorporated in the summary statistics of the scheduled visits.
- Biomarker research samples are taken prior to rituximab infusion.

Table 2: Time and events schedule

	Screening	Month 0	Month 1.5	Month 3	Month 4 (R)	Month 8	Month 12	Month 16	Month 20	Month 24	Month 27	Month 30	Month 36	Month 42	Month 48	Unscheduled Visit
Forms																
Enrolment	X															
Demographics	X															
Weight	X				X											
Height	X															
Urinary HCG		X														
Baseline Medical History	X															
Comorbidities	X															
Concomitant Medication	X	X	X	X	X											X
Follow Up		X	X	X	X	X	X	X	X	X	X	X	X	X	X	X
Treatment		X			X	X	X	X	X							
BVAS/WG		X	X	X	X	X	X	X	X	X	X	X	X	X	X	X
CDA		X			X		X			X			X	X	X	X
SF-36, EQ5D		X			X		X			X			X	X	X	X
PROMIS questionnaires	X	X	X	X	X	X	X	X	X	X	X	X	X	X	X	X
Adverse event review		X	X	X	X											

	Screening	Month 0	Month 1.5	Month 3	Month 4 (R)	Month 8	Month 12	Month 16	Month 20	Month 24	Month 27	Month 30	Month 36	Month 42	Month 48	Unscheduled Visit
Clinical Labs																
FBC/CBC	X	X	X	X	X	X	X	X	X	X	X	X	X	X	X	X
ESR	X	X	X	X	X	X	X	X	X	X	X	X	X	X	X	X
Chemistry (electrolytes, creatinine, LFTs)	X	X	X	X	X	X	X	X	X	X	X	X	X	X	X	X
CRP	X	X	X	X	X	X	X	X	X	X	X	X	X	X	X	X
ANCA	X	X	X	X	X	X	X	X	X	X	X	X	X	X	X	X
Urinalysis	X	X	X	X	X	X	X	X	X	X	X	X	X	X	X	X
Lymphocyte markers		X	X	X	X	X	X	X	X	X	X	X	X	X	X	X
Immunoglobulins		X	X	X	X	X	X	X	X	X	X	X	X	X	X	X
Hepatitis B	X															
Research samples																
Serum		X			X	X	X	X	X	X	X	X	X	X	X	X
Plasma		X			X	X	X	X	X	X	X	X	X	X	X	X
DNA		X														
RNA		X			X					X			X			

## 7 Sample Size

(ICH E3; 9.7.2. ICH E9; 3.5)

Enrolment will be ongoing until 160 patients are randomised. It is anticipated 190 patients will be required to be recruited to meet the goal of 160 patients randomized. Any patients in the induction phase when enrolment is halted will continue to follow the protocol and be randomised if the relevant criteria are met.

A power of 90% is achieved under the alternative hypothesis of a hazard ratio of 0.42 at the 5% significance level with 58 observed relapses. Randomising 160 patients will achieve this over the course of the study assuming a drop-out rate up to 5% at 2 years and a relapse-free rate of 75% and 50% at 4 years in the experimental and control arms respectively.

Based on data from the Cambridge cohort study, the overall hazard ratio is estimated (95% confidence interval) as 0.230 (0.116, 0.458) based on 37 observed relapses. For the early period the hazard ratio estimate is 0.210 (0.098, 0.449) based on 30 observed relapses. For the late period the hazard ratio estimate is 0.323 (0.061, 1.729) based on seven observed relapses. Hence the sample size/power calculations are robust as they are based on a hazard ratio of 0.42 under the alternative hypothesis; the value of 0.42 is at the upper end of the confidence intervals for the overall and early period hazard ratios from the pilot data. The projected drop-out rate is based on the recently published EUVAS IMPROVE trial (16). It justifies the assumption of a rate below 5% in the second year.

## 8 General Considerations

### 8.1 Timing of Analyses

The trial is planned to close 36 months after the final patient is enrolled. All those eligible who have been randomised and entered into the maintenance phase of the trial will be followed until the last patient to be enrolled has completed 36 months from study entry. The maintenance phase analysis will be performed after the last enrolled patient (excluding drop-outs) has reached Month 36 visit, this is the common close of the trial.

The statistical analysis plan (SAP) will be approved according to the requirements of CCTU/SOP023 before database lock. Permission to lock the database will be requested from the chief investigator (CI) using CCTU/FRM094, and the data programmers will deposit the data in a folder to which the trial statistician is given restricted access (following CCTU/SOP057).

An independent adjudication committee (blinded to treatment) will review all relapses prior to analysis and any changes deemed necessary will be recorded and included into MACRO database. Data queries will be referred to the data management team for resolution (using CCTU/TPL064).

## 8.2 Analysis Populations

(ICH E3; 9.7.1, 11.4.2.5. ICH E9; 5.2)

Prior to database lock, each patient will be included or excluded from each analysis population defined below. The trial management team will agree on inclusion to each population prior to the analysis.

### 8.2.1 Safety Population

The safety population comprises all consented subjects enrolled in the trial, regardless of whether they achieved remission and were randomised at month 4. The treatment group will be analysed as randomised (rituximab or azathioprine), patients who were enrolled but not randomised will be classified as belonging to the induction group (induction).

### 8.2.2 Full Analysis Population (randomised patients)

The full analysis population is defined as all participants who achieved remission in the induction phase of the trial and were randomised to the maintenance phase, regardless of whether they actually received any maintenance treatment. The treatment group will be analysed as randomised (rituximab or azathioprine).

### 8.2.3 Per Protocol Populations (maintenance and follow-up)

The per-protocol populations includes all randomised patients who have not deviated from protocolised treatment either during the maintenance phase of the trial (from randomisation to month 24) or follow-up (from randomisation to end of

---

 Details of data utilised in the formal relapse adjudication process can be found in a separate document [reference].

trial). Thus two per-protocol populations will be defined: maintenance compliant and follow-up compliant. It is assumed that maintenance compliance is necessary for follow-up compliance, and the two per-protocol populations will be defined using this inclusive criterion. Patients who withdraw from trial or from protocolised treatment will be assessed for compliance up to the point of their withdrawal.

Compliance to the protocol of all trial treatments (rituximab, azathioprine, methotrexate, and mycophenolate Mofetil) will be considered, according to the randomised treatment allocation (rituximab or azathioprine schedules). Compliance to prednisolone schedule is not considered. In the case of treatment of relapse, what treatments are in accordance with the protocol are detailed in Section 11.6 of the protocol:

*Patients experiencing their first minor relapse after randomisation and before month 24 of the treatment phase will remain on the randomised treatment (rituximab or azathioprine) and will have their oral prednisolone/prednisone increased to 20mg/day for one week decreasing in 2.5mg increments each week to reach 5mg/day after six weeks. The second minor relapse or first major relapse, occurring before month 24 of the treatment phase will result in the patient being withdrawn from protocolised treatment and returned to treatment according to local best practice. Any relapse occurring after the 24 month treatment phase will be treated according to local best medical practice.*

Due to the complexity of the data involved, each patient course of treatments will be assessed individually and an independent adjudication committee (blinded to subject ID) will determine each patient's inclusion/exclusion in the per protocol population base on data taken from the Treatment Form, Follow-Up Form and Relapse Form. It is expected that these data be reviewed concurrently with the formal adjudication of relapses and incorporated into the trial's database prior to hard lock.

---

 Details of data used to assess inclusion in the per-protocol populations can be found in document "Medication Compliance v 1.0" and a separate report will be produced by the independent adjudication committee detailing each patient's assessment and outcome.

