## 9 Trial Design

### 9.1 Statement of Design

RITAZAREM is a multi-centre, international, open label, randomised controlled trial in relapsing AAV. Patients will be randomised, 1:1, to receive fixed interval repeat rituximab dosing or azathioprine maintenance therapy.

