**Table 1: Censoring rules**

Situation	Date of Relapse or Censoring	Outcome
No baseline assessments	Randomization	Censored
Relapse documented between scheduled visits	Unscheduled visit date	Relapsed
Drop-out with no relapse	Date of last assessment with no documented relapse	Censored
Treatment discontinuation for undocumented relapse	Date of last assessment with no documented relapse	Censored
Treatment discontinuation for toxicity or other reason, or protocol deviation	The patient will be followed up as per protocol and date of relapse or censoring observed accordingly	Relapsed/censored
Death due to relapse	Date of Death	Relapsed
Death due to other causes	Date of Death	Censored
Death or progression after more than one missed visit	Date of last assessment with no documented relapse	Censored

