## 10 Efficacy Analyses

Efficacy analyses will be performed on the full analysis population. Additionally the primary efficacy analysis will be presented for the two per-protocol populations (maintenance and follow-up compliant populations).

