### 10.1 Primary efficacy analysis

The primary efficacy outcome measure of the trial is relapse-free survival, where a relapse is either major or minor (see definitions above). **The primary analysis will be a Cox regression model adjusted for the stratification factors (ANCA type, relapse severity and prednisone induction regimen) for the difference in the distribution of relapse-free survival between the rituximab arm and the azathioprine (control) arm (two-sided at  $\alpha$ -level of 5%).** Assuming a proportional hazard holds, the hazard ratio together with the 95% confidence interval will be estimated using a Cox regression model adjusted for the stratification factors.

There will be a closed testing procedure, first the null hypothesis will be tested for a hazard ratio of 1 at all time points. If this is rejected at a 5% level then two further sub-hypothesis will be examined using time-varying covariates:

1. A hazard ratio of 1 up to 20 months post-randomisation (i.e. during treatment).
2. A hazard ratio of 1 after 20 months post-randomisation (i.e. post-treatment).

Kaplan-Meier estimates for relapse-free survival at 24 and 48 months and median relapse-free survival with the corresponding 95% confidence intervals by treatment allocation will be presented.

Additional analyses will consider in turn the interaction of treatment with each of the three stratification variables, i.e. ANCA type, relapse severity and induction regimen. Frequency tables and Kaplan-Meier plots, as well hazard ratios and 95%

---

 Time measured from enrolment, in reality this corresponds to 20 months and 44 months post-randomisation.

confidence intervals of a Cox proportional hazard model including interactions will be presented. These results are to be taken as exploratory only, as these analyses were not planned in the protocol, are likely under-powered and are not adjusted for multiple comparisons.

The following tables and figures will be reported, taking into account events occurring after randomisation (i.e. excluding the induction phase):

- No. of relapses:
  - a) by type (major or minor)
  - b) by phase (during treatment or post-treatment)
  - c) per participant
- No. of participants with a relapse (major or minor) by type at:
  - a) All time points
  - b) During treatment (up to month 20 post-randomisation)
  - c) Post-treatment (after 20 months post-randomisation)

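### Per-protocol compliance is judged beyond the first relapse, so a patient with an early minor relapse can be excluded, together with the primary event, for what happened afterwards

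*SAP*

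**What the plan says.** The primary endpoint is time from randomisation to the first relapse, major or minor (SAP 5.2.1 and 10.1). Efficacy is analysed in the full analysis population, and SAP 10 adds: "Additionally the primary efficacy analysis will be presented for the two per-protocol populations".

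SAP 8.2.3 defines two nested per-protocol populations: no deviation from protocolised treatment from randomisation to month 24, and none from randomisation to the end of the trial. Rituximab, azathioprine, methotrexate and mycophenolate count; the prednisolone schedule does not. Treatment of relapse is part of the assessment: "In the case of treatment of relapse, what treatments are in accordance with the protocol are detailed in Section 11.6 of the protocol". The section then reproduces Protocol 11.6 and lists the Relapse Form among the committee's sources.

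Two further rules matter. On withdrawal, SAP 8.2.3 says: "Patients who withdraw from trial or from protocolised treatment will be assessed for compliance up to the point of their withdrawal". For patients who discontinue for toxicity, another reason or a protocol deviation, SAP Table 1 says: "The patient will be followed up as per protocol and date of relapse or censoring observed accordingly". Nothing in SAP 8.2.3 or 10 ends the compliance assessment at the first relapse.

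**The concern.** A patient's contribution to a time-to-first-relapse analysis is complete at the first relapse. If membership of the analysis set depends on treatment after that date, patients can be removed because of what followed the event, and the event goes with them. Only patients who have relapsed can be removed in this way.

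The trial is open label, so the investigator who decides what to do after a minor relapse knows the arm. The compliance committee is described as blinded to subject ID, whereas the relapse committee is described as blinded to treatment (SAP 8.1 and 10.3). Compliance has to be judged against the allocated schedule, so nothing stated hides the arm at that step either. If departures after a minor relapse are more common in one arm, that arm loses more events.

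At stake is how the two per-protocol results can be read. They are the only adherence-based analyses of the primary endpoint that the SAP states. The primary result is not at stake.

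**Working it through.** **Step 1. Who is exposed.** Setting SAP 8.2.3 beside the Protocol 11.6 text that it reproduces:

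| Situation | Status under the rules | Effect on membership |
|---|---|---|
| First major or second minor relapse before month 24 | Withdrawn from protocolised treatment; local treatment accords with the protocol | Not removed for it |
| Any relapse after month 24 | Local treatment accords with the protocol | Not removed for it |
| Steroid departure after any relapse | Not considered | Not removed for it |
| First minor relapse before month 24, then a non-steroid change, withdrawal recorded | Assessed only up to withdrawal | Can stay, with the event |
| Same, no withdrawal recorded | Randomised treatment was to continue, so this is a deviation | Can be excluded, with the event |

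Only the last row is a problem. It covers a switch of agent and also later randomised treatment not given per protocol.

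**Step 2. The planning figure.** The SAP states: "A power of 90% is achieved under the alternative hypothesis of a hazard ratio of 0.42 at the 5% significance level with 58 observed relapses". The test is two-sided (SAP 10.1) and allocation is 1:1. Schoenfeld: 4 × (1.960 + 1.282)² / (ln 0.42)² = 55.9, so 56 events. Power with 58 events: Φ(√58/2 × 0.8675 − 1.960) = Φ(1.343) = 0.910. The stated figures are reproduced.

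**Step 3. Hazards and expected events.** The SAP plans on 160 randomised, "assuming a drop-out rate up to 5% at 2 years and a relapse-free rate of 75% and 50% at 4 years". With exponential times:
- control hazard = ln 2 / 48 = 0.01444 per month
- rituximab hazard = −ln 0.75 / 48 = 0.00599 per month
- ratio = 0.415
- drop-out hazard δ = −ln 0.95 / 24 = 0.00214 per month

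Events per arm by time T = 80 × λ/(λ+δ) × (1 − exp(−(λ+δ)T)). At T = 48 the two arms give 57.3, close to the 58 planned. Follow-up of 36–48 months from entry is 32–44 months from randomisation. Spread uniformly (assumption), it gives 32.5 control and 15.7 rituximab events, about 48 in all. By 20 months after randomisation (month 24) the formula gives 19.7 + 8.9, about 28.5.

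**Step 4. Removing exposed patients.** Assumptions not in the documents: 50–70% of first relapses are minor, and 10–50% of the early minor ones are treated off protocol with no withdrawal recorded.

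One case by hand (70% minor; removal 10% rituximab, 50% control). Control loses 19.67 × 0.7 × 0.5 = 6.88 events and rituximab 8.85 × 0.7 × 0.1 = 0.62. Person-time is events divided by hazard: 2,251 and 2,612 months. Those removed had contributed about 9.4 and 9.7 months each. Rates become 25.63/2,186 = 0.01172 and 15.04/2,606 = 0.00577, ratio 0.49. An unadjusted Cox fit gives 0.48; the difference reflects early-only removal and simulation error.

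Cox results, 400,000 simulated patients per row, removals scaled to 160:

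| Minor share | Removal, rituximab / control | Events removed | Full-analysis HR | Per-protocol HR |
|---|---|---|---|---|
| 50% | 20% / 20% | 2.9 | 0.415 | 0.413 |
| 50% | 50% / 50% | 7.2 | 0.415 | 0.411 |
| 50% | 10% / 30% | 3.4 | 0.414 | 0.436 |
| 50% | 10% / 50% | 5.4 | 0.412 | 0.460 |
| 50% | 30% / 10% | 2.3 | 0.416 | 0.392 |
| 50% | 50% / 10% | 3.2 | 0.417 | 0.369 |
| 70% | 20% / 20% | 4.0 | 0.415 | 0.413 |
| 70% | 50% / 50% | 9.9 | 0.418 | 0.414 |
| 70% | 10% / 30% | 4.7 | 0.420 | 0.451 |
| 70% | 10% / 50% | 7.6 | 0.410 | 0.483 |
| 70% | 30% / 10% | 3.2 | 0.414 | 0.379 |
| 70% | 50% / 10% | 4.5 | 0.413 | 0.344 |

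The full-analysis column varies around 0.415 only through simulation error.

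**Step 5. Patients who stop without relapse.** Assume 10% or 20% per arm stop at a uniform time in the 20 months, rituximab stoppers take the control hazard and control stoppers keep theirs (60% minor, 20% removal in both arms). The full-analysis HR is 0.448 or 0.493, the per-protocol HR that keeps them 0.447 or 0.491, and the HR with them excluded 0.410 or 0.416.

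**The case against.** The strongest reply is that few patients are affected. The sentence on relapse treatment mostly protects relapsers, because it makes local treatment acceptable after most relapses. A withdrawal form exists with relapse and investigator decision among its reasons (SAP 9.1.2, Table 3); once it is completed, the patient and the event can stay. If that halves a 30% v 10% imbalance to 15% v 5%, control loses 19.67 × 0.5–0.7 × 0.15 = 1.5–2.1 events and the hazard ratio is only 0.42–0.43. Membership is decided case by case, and the separate medication compliance document may settle these cases. Per-protocol results are additional, and adherence is also described in SAP 9.9 and 9.10.

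Most of this stands and sets the limits of the point. It does not remove it. Patients with no recorded withdrawal remain exposed, so the same change of treatment can count as compliant or not depending on whether a form was filled in. The compliance document is not available here, and a rule that fixes an analysis population belongs in the SAP.

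A reader might infer that any off-protocol treatment after a first relapse removes the patient. Step 1 shows that it does not. A reader might also take the retained stoppers as a second bias created by the per-protocol rule. The same patients are in the full analysis population, and Step 5 shows the two hazard ratios nearly equal. The dilution there also depends on the assumption about control stoppers: if their hazard rises 1.5- to 2-fold, the hazard ratio that keeps them is 0.43–0.46.

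**Conclusion.** The point holds in a narrow form. SAP 8.2.3 lets treatment after the primary event decide membership, for patients with a first minor relapse before month 24 and no recorded withdrawal. Under the assumptions in Step 4, 2 to 10 of about 48 first relapses would be lost. If removal differs by arm, the per-protocol hazard ratio can move either way, from about 0.34 to 0.48 against 0.415. If removal is equal, it stays at 0.411–0.414.

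It would be tempting to say that the per-protocol hazard ratio is biased, or biased towards no effect. The documents do not support that: they give no removal rates, and which arm loses more events is a guess. The full-analysis result does not change.

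Separately, the withdrawal clause together with Table 1 lets patients who stop without relapse count as compliant while contributing time off treatment. This brings the per-protocol result close to the full-analysis result. It limits interpretation and is a different matter from lost events.

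**What to change.** In SAP 8.2.3, and by reference in SAP 10, state that for the per-protocol analyses of time to first relapse, compliance is judged from randomisation to the earlier of the first adjudicated relapse or the censoring date, within each population's window, and that treatment after that date is ignored. No primary event can then be lost for post-relapse treatment. The full analysis does not change.

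The cost is the wording, one date comparison in the code and a recheck. SAP 9.9 describes the assessment as done and recorded as yes/no with reasons, so deviation dates must be checked for every non-compliant patient who relapsed. On the figures above, those affected are few.

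For patients who stop without relapse, say in SAP 8.2.3 that they are retained and that the per-protocol result will therefore resemble the full-analysis result. Censoring at withdrawal is at most an optional sensitivity analysis. Stopping may be related to relapse risk and may differ by arm in an open-label trial, so the assumption of non-informative censoring would have to be stated.

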### 9.6 Trial Endpoints

#### 9.6.1 Primary endpoint

The primary endpoint is the time to disease relapse (either minor or major relapse) from randomisation. Any patients who have not relapsed at study close will be censored. Further details of how relapse/censoring dates will be defined are given below.

A blinded Independent Adjudication Committee will be convened to look at all endpoint data.

Situation	Date of Relapse or Censoring	Outcome
No baseline assessments	Randomization	Censored
Relapse documented between scheduled visits	Unscheduled visit date	Relapsed
Drop-out with no relapse	Date of last assessment with no documented relapse	Censored
Treatment discontinuation for undocumented relapse	Date of last assessment with no documented relapse	Censored
Treatment discontinuation for toxicity or other reason, or protocol deviation	The patient will be followed up as per protocol and date of relapse or censoring observed accordingly	Relapsed/censored
Death due to relapse	Date of Death	Relapsed
Death due to other causes	Date of Death	Censored
Death or progression after More than one missed visit	Date of last assessment with no documented relapse	Censored

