## 10.5 Method of Blinding

This will be an open label study.

A non-blinded, open label study has been chosen for *reasons of simplicity and practicality* in view of RITAZAREM being an international multi-centre trial. Previous EUVAS studies with similar end-points have also been unblinded yet have led to robust and reproducible conclusions.

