### 9.10.1 Rituximab treatment

---

 See *Medication Compliance.docx*

 See section 11.2 of the protocol for further details of azathioprine administration.

The Treatment form records details of rituximab treatment, at months 4, 8, 12, 16 and 20, as recorded by the PI. The form will be reported at each time point using the full analysis population. The following variables will be summarised in accordance with section 9:

- Rituximab dose (mg)
- Rituximab administered according to protocol (Yes/No)
- Reasons for non-compliance, counts:
  - a) Rituximab not administered as IgG < 3g/L
  - b) Incomplete
  - c) Interrupted
  - d) Other

Reasons given for incomplete/interrupted/other treatment non-compliance will be listed per patient, per visit.

In addition, total cumulative rituximab dose after 24 months as recorded in the Follow Up form as well as the following derived variable (details in section 9.2) will be calculated across the maintenance therapy period and summarised in accordance with section 9:

- Cumulative rituximab dose (mg) up to 24 months
- Total rituximab dose in maintenance phase (mg) – derived variable, details in section 9.2
- Overall full rituximab treatment (Yes/No) – derived variable, details in section 9.2
- Number of full rituximab infusions – derived variable, details in section 9.2

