Events happening between 6 and 12 months of the censoring date require further investigation. Depending on the last visit before any missing gaps, these events could fall after either one or two missed visits (e.g. an event 200 days after month 30 would happen after one missed visits, while an event 200 days after month 24

would happen after two missed visits). Thus the 12 months threshold is not strong enough to determine the outcome. The analysis code explicitly checks for such instances, which must then be adjudicated independently. None were found.

Likewise, by inspection, all deaths were by other causes and occurred before more than one missed visit, and thus no special considerations are needed (all patients who died were censored at the time of death).

An independent adjudication committee (blinded to treatment) will review all relapses and deaths. This will ensure that “deaths due to relapse” are recorded in the trial database as a relapse (i.e. there exists a corresponding relapse form). The censoring date of “deaths due to other causes” will also be verified in cases with more than one missed visit.

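### SAP 8.2.3 runs an arm-revealing compliance review alongside the treatment-blinded relapse adjudication, with no stated order, lock or separation, so the only blind on the primary endpoint is at risk and cannot be verified

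*SAP*

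**What the plan says.** Protocol 10.5 states: "This will be an open label study". Protocol 9.6.1 then sets up the safeguard for the endpoint: "A blinded Independent Adjudication Committee will be convened to look at all endpoint data". The SAP specifies that blind twice. Section 8.1 says "An independent adjudication committee (blinded to treatment) will review all relapses prior to analysis", and adds that changes judged necessary go into the trial database. Section 10.3 says "An independent adjudication committee (blinded to treatment) will review all relapses and deaths".

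SAP 8.2.3 describes a second review. Per-protocol status is decided by "an independent adjudication committee (blinded to subject ID" and no more; masking to treatment is not mentioned. Compliance is assessed "according to the randomised treatment allocation (rituximab or azathioprine schedules". The sources are the Treatment, Follow-Up and Relapse Forms. On timing, the section says "It is expected that these data be reviewed concurrently with the formal adjudication of relapses", with the results entered before hard lock.

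Two of those forms reveal the arm. SAP 9.10.1 says: "The Treatment form records details of rituximab treatment, at months 4, 8, 12, 16 and 20". SAP 9.10.2 lists the Follow-Up Form items, which include rituximab, azathioprine, methotrexate and mycophenolate.

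**The concern.** Investigators identify relapses knowing the arm. A minor relapse, meaning any rise in disease activity short of a major relapse, counts fully towards the primary endpoint. Treatment-blinded adjudication is what stands between that knowledge and the hazard ratio, and the committee can change relapse status.

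The compliance review cannot be blind to treatment, because it compares what each patient received with the schedule of the randomised arm. Scheduling it alongside the relapse adjudication leaves a route by which someone still deciding relapses could learn the arm. If that happened, confirmations and overturns could differ between arms and bias the comparison in either direction.

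**Working it through.** **The two reviews side by side**

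| | Relapse adjudication (SAP 8.1, 10.3) | Compliance review (SAP 8.2.3, 9.9) |
|---|---|---|
| Body | independent adjudication committee | independent adjudication committee (8.2.3 and footnote 4); independent committee (9.9) |
| Masked to | treatment | subject ID only (8.2.3); nothing stated (9.9) |
| Data | in a separate document, not supplied (footnote 3) | Treatment, Follow-Up and Relapse Forms; detail in a separate document, not supplied (footnote 4) |
| Timing | before analysis | concurrent with relapse adjudication, before hard lock |
| Order, lock or separate panels | not stated | not stated |

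Three things follow.

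1. Whoever does the compliance review sees the arm.
2. Nothing in the text stops the same people from deciding relapses in the same period. The near-identical naming of the committee suggests overlap but does not establish it.
3. Masking the subject ID would hinder linking the two files. However, the Relapse Form is a compliance source, and SAP 5.2.1 takes the relapse time from it. If that form is also in the relapse pack, files could be matched on dates and course. Its presence there is likely but not stated.

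The SAP's own compliance rule also points to an order. SAP 8.2.3 quotes Protocol 11.6, under which a first minor relapse before month 24 leaves the patient on randomised treatment, while a major or second minor relapse takes the patient off protocolised treatment. Compliance is assessed up to that withdrawal. Whether a course of treatment complied therefore depends on relapse type, which adjudication is meant to settle.

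**The plan's design figure (context only; not disputed)**

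Inputs from SAP 7 and 10.1: hazard ratio 0.42, two-sided 5%, 90% power, 58 relapses, 1:1 allocation. Schoenfeld: 4 × (1.960 + 1.282)² / (ln 0.42)² = 56 events. Power at 58 events is 91.0%. The stated 58 is reproduced closely.

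**Illustration 1: hazard ratio**

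Inputs: 160 randomised 1:1, so 80 per arm; 4-year relapse-free rates of 75% and 50% (SAP 7), so 80 × 0.25 = 20 rituximab and 80 × 0.50 = 40 control relapses. Drop-out is ignored. The overturn counts are assumptions. HR ≈ ln(1 − e_R/80) / ln(1 − e_C/80).

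| Scenario | e_R | e_C | HR |
|---|---|---|---|
| Plan's rates | 20 | 40 | 0.415 |
| 3 rituximab relapses overturned | 17 | 40 | 0.345 |
| 3 control relapses overturned | 20 | 37 | 0.463 |
| No true effect | 30 | 30 | 1.00 |
| No true effect, 5 rituximab relapses overturned | 25 | 30 | 0.797 |

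**Illustration 2: type I error**

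Assume no true effect, 58 investigator-reported relapses, and a share q rejected in one arm only. The expected hazard ratio is then 1 − q and the event count is e = 58(1 − q/2). With z = √(e/4) × |ln(1 − q)|, the two-sided error is Φ(z − 1.96) + Φ(−z − 1.96). For q = 10%: e = 55.1, z = √13.775 × 0.1054 = 0.391, error 6.8%.

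| q | Type I error |
|---|---|
| 0 | 5.0% |
| 5% | 5.4% |
| 10% | 6.8% |
| 20% | 12.7% |
| 30% | 24.0% |

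**The case against.** A reader might infer that the blind cannot hold, or that it was broken. The documents do not support that, for four reasons.

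- **Membership.** No section says the same people do both reviews. Two different blinds are consistent with two panels, and SAP 9.9 mentions only an independent committee. Footnote 4 uses the definite article, but it may refer back to the body named in 8.2.3.
- **Timing.** The sentence goes on to entry in the database before hard lock. Concurrent may mean the same calendar window rather than the same sitting or open relapse decisions.
- **Linkage.** The contents of the relapse pack are in a document not supplied. That the Relapse Form is in both packs is an inference.
- **Size.** Every overturn count above is assumed and one-sided. At modest levels the effect is small: 5.4% type I error if 5% of one arm's relapses are rejected.

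It is also fair to say that judgement is constrained: relapse is defined by new BVAS/WG items, and the form is itemised and scored automatically.

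All of this stands as a limit on the claim, but it does not remove the concern. The SAP goes beyond silence: it sets a concurrent timetable for a review that shows the arm, and it states nothing that keeps that information from those deciding relapses. Itemised scoring does not make adjudication mechanical either, since the committee is there to change relapse decisions where needed.

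**Conclusion.** The concern holds as a design weakness. The SAP schedules two reviews with different blinds at the same time and states no separation of panels, order or lock. The only blind described for the primary endpoint is therefore at risk, and a reader cannot confirm from the documents that it was kept. The masking mentioned in SAP 11.1 concerns serious adverse event review and does not help here.

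What the text establishes is the open-label design, the treatment-blinded adjudication, the arm-revealing compliance data and the concurrent timing. Overlap of members and of the Relapse Form is likely but unproven. The shifts from 0.415 to 0.345 or 0.463, and the type I error of 6.8% at 10% one-arm rejection, show what differential adjudication could do; they do not estimate what happened. The sample size and significance level are unaffected.

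**What to change.** In SAP 8.2.3, change *concurrently with* to *after*. State that every relapse and death decision (occurrence, type and date) is signed and locked before any Treatment Form or Follow-Up Form dosing data are released for the compliance review, and is not reopened afterwards. Make the adjudication working document agree. The same people can then do both tasks in sequence, so no extra assessors are needed, and compliance is judged against a settled relapse type.

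SAP 9.9 describes the compliance assessment in the past tense. If both reviews are already complete, rewording the timing would misdescribe them. In that case report whether the panels were the same, the order of review, and every relapse decision changed after treatment data had been seen.

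The cost is one sentence in the SAP with a matching line in the working document, and possibly a short delay before hard lock. If the reviews are finished, the cost is a short disclosure instead.
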